12.3.2 Attribution Definitions

The relationship, or attribution, of an adverse event to the study therapy regimen or study procedure(s) will initially be determined by the site investigator and recorded on the appropriate AE paper case report form (AE/SAE paper CRF). Final determination of attribution for safety reporting will be determined by DAIT/NIAID. The relationship of an adverse event to study therapy regimen or procedures will be determined using the descriptors and definitions provided in Table 12.3.2.

For additional information and a printable version of the NCI-CTCAE manual, consult the NCI-CTCAE web site: <http://ctep.cancer.gov/reporting/ctc.html>.

Table 12.3.2 Attribution of Adverse Events

Code	Descriptor	Definition (guidelines)
UNRELATED CATEGORY		
1	Unrelated	The adverse event is clearly not related to study. The event is completely related to an etiology other than the study product or study intervention (the alternative etiology must be documented in the study subject's medical record)
2	Unlikely	The adverse event is doubtfully related to study and likely to be related to factors other than study product or study intervention.
RELATED CATEGORIES		

3	Possible	The adverse event may be related to study. There is an association between the event and the administration of study product and there is a plausible mechanism for the event to be related to the study product; there may be also an alternative etiology, such as characteristics of the subject's clinical status and/or underlying disease
4	Probable	The adverse event is likely related to study. There is (1) an association between the event and the administration of study product or study intervention, (2) a plausible mechanism for the event to be related to the study product, and (3) the event could not be reasonably explained by known characteristics of the subject's clinical status and/or an alternative etiology is not apparent
5	Definite	The adverse event is clearly related to study. There is (1) an association between the event and the administration of the study product or study intervention, (2) a plausible mechanism for the event to be related to the study product, and (3) causes other than the study product have been ruled out and/or the event re-appeared on re-exposure to the study product

12.4 Collection and Recording of Adverse Events

12.4.1 Collection Period

Adverse events will be collected from the time of enrollment, until a subject completes study participation or until 14 days after he/she prematurely withdraws (without withdrawing consent) or is withdrawn from the study if the subject has received study medication or has undergone aspirin challenge.

12.4.2 Collecting Adverse Events

Adverse events (including SAEs) may be discovered through any of these methods:

- Observing the subject.
- Interviewing the subject with specific questions about whether there has been any change in health status.
- Receiving an unsolicited complaint from the subject.
- Notification through the hospital medical record
- In addition, an abnormal value or result from a clinical or laboratory evaluation can also indicate an adverse event, as defined in Section 12.3, *Grading and Attribution of Adverse Events*.

12.4.3 Recording Adverse Events

Throughout the study, the investigator will record adverse events and serious adverse events as described previously on the appropriate paper case report form (AE/SAE paper CRF) regardless of the relationship to study therapy regimen or study procedure.

Once recorded, an AE/SAE will be followed until it resolves with or without sequelae, or until the end of study participation, or until 14 days after the subject prematurely withdraws (without withdrawing consent)/or is withdrawn from the study, whichever occurs first.

12.5 Reporting of Serious Adverse Events and Adverse Events

12.5.1 Reporting of Serious Adverse Events to Sponsor (DAIT/NIAID)

This section describes the responsibilities of the site investigator to report serious adverse events to the sponsor via *email*. Timely reporting of adverse events is required by 21 CFR and ICH E6 guidelines.

Site investigators will report all serious adverse events to the sponsor in any of the “related” categories (see Section 12.2.3, *Serious Adverse Event*), regardless of expectedness within 24 hours of discovering the event.

For serious adverse events, all requested information on the AE/SAE paper CRF will be provided. However, unavailable details of the event will not delay submission of the known information. As additional details become available, the AE/SAE paper CRF will be updated and submitted.

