11.5. Study Stopping Rules

The study may be prematurely terminated for the following reasons:

The Study PI or ISM may terminate this study at any time. Reasons for termination may include, but are not limited to the incidence or severity of AEs in this study indicating a potential health hazard to subjects or unsatisfactory subject enrollment. Any serious and/or persistent noncompliance by the investigator with the protocol, the clinical research agreement, the Form FDA 1572, or other local applicable regulatory guidelines in conducting the study may also be grounds for termination of the study. The PI will promptly inform all other investigators conducting the study if the study is suspended or terminated for safety reasons and will also inform the regulatory authorities of the suspension or termination of the study and the reason(s) for the action.

Study enrollment, investigational drug, and study procedures will be suspended pending expedited review of all pertinent data by the IRB and the NIAID, if any one of the following occurs:

1. If any death occurs that is designated as related to ifetroban or to a study procedure

2. If 3 AERD enrolled trial participants experience serious non-fatal AEs related to aspirin desensitization, or if 2 AERD enrolled participants experience serious non-fatal AEs related to ifetroban/placebo, or to another study procedure.

12. Safety Monitoring and Reporting

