12.1 Overview

This section defines the types of safety data that will be collected under this protocol and outlines the procedures for appropriately collecting, grading, recording, and reporting those data. Adverse events that are classified as serious according to the definition of health authorities must be reported promptly (per Section 12.5, *Reporting of Serious Adverse Events and Adverse Events*) to the sponsor DAIT/NIAID. Appropriate notifications will also be made to site principal investigators, Institutional Review Boards (IRBs), and health authorities.

Information in this section complies with *ICH Guideline E2A: Clinical Safety Data Management: Definitions and Standards for Expedited Reporting*, *ICH Guideline E-6: Guideline for Good Clinical Practice*, 21CFR Parts 312 and 320, and applies the standards set forth in the National Cancer Institute (NCI), Common Terminology Criteria for Adverse Events (CTCAE), Version 4.0: <http://ctep.cancer.gov/reporting/ctc.html>.

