12.8 Review of Safety Information

12.8.1 Medical Monitor Review

The DAIT/NIAID Medical Monitor shall receive monthly reports from the *Principal Investigator* compiling new and accumulating information on AEs, SAEs, and pregnancies recorded by the study site on appropriate paper CRFs.

In addition, the Medical Monitor shall review and make decisions on the disposition of the SAE and pregnancy reports received by the *Principal Investigator* (See *Reporting of Serious Adverse Events to Sponsor*, and *Pregnancy Reporting*).

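### The 24-hour SAE duty in 12.5.1 covers only events the site codes as related, and Section 12.5 sets no deadline for the rest, although the sponsor makes the final attribution

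*Combined protocol and SAP*

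**What the plan says.** - **12.1 Overview:** "Adverse events that are classified as serious according to the definition of health authorities must be reported promptly" to DAIT/NIAID. The sentence has no relatedness limit and refers to Section 12.5 for the procedure.
- **12.5.1:** "Site investigators will report all serious adverse events to the sponsor in any of the" related categories, "regardless of expectedness within 24 hours of discovering the event". It cites 12.2.3 for those categories, but 12.2.3 defines seriousness. The categories are in Table 12.3.2, where possible, probable and definite count as related, and unrelated and unlikely do not.
- **12.3.2:** Attribution "will initially be determined by the site investigator". Then: "Final determination of attribution for safety reporting will be determined by DAIT/NIAID".
- **12.4.3:** The site records AEs and SAEs on the case report form whatever their relationship to treatment or procedures.
- **12.8.1:** The DAIT/NIAID Medical Monitor "shall receive monthly reports" compiling AEs, SAEs and pregnancies.
- **12.8.2.1:** The ISM reviews all SAEs. The only interval given is at least yearly.
- **11.5 Study Stopping Rules:** Suspension pending review follows "If any death occurs that is designated as related to ifetroban or to a study procedure", or "If 3 AERD enrolled trial participants experience serious non-fatal AEs related to aspirin desensitization", or if 2 participants have serious non-fatal AEs related to ifetroban/placebo or to another study procedure.

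**The concern.** The 24-hour duty depends on the judgment that the sponsor is meant to check. If the site codes an SAE as related and the sponsor disagrees, the sponsor has the report within a day. If the site codes it as unrelated or unlikely and the sponsor would disagree, nothing in Section 12.5 requires the report to arrive by any stated time. The second error is the one that matters for safety, and it is the one checked slowly.

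Several later steps depend on relatedness: expedited reporting (12.5.2.2), the ad hoc ISM and DSMB reviews (12.8.2.2 and 12.8.3.2), the enrollment halt tied to an ad hoc DSMB review, and the suspension counts in 11.5. Where the sponsor's attribution feeds one of these, late receipt delays it, while dosing and aspirin challenges continue.

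**Working it through.** The plan has no statistical figure to reproduce here. The check is a comparison of sections, plus simple arithmetic for the size of the delay.

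**Step 1. Follow an SAE by the site's code.**

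| | Coded possible, probable or definite | Coded unrelated or unlikely |
|---|---|---|
| Recorded at site (12.4.3) | yes | yes |
| Deadline to sponsor (12.5.1) | 24 hours | none stated |
| Scheduled sponsor route (12.8.1) | monthly report as well | monthly report |
| ISM (12.8.2.1) | all SAEs, at least yearly | all SAEs, at least yearly |

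**Step 2. Compare 12.1 with 12.5.1.** Section 12.1 covers all serious events and says promptly; 12.5.1 covers a subset and says 24 hours. Because 12.1 defers to 12.5, and 12.5 is silent on the remainder, the result is a mismatch of scope and a missing timeline.

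**Step 3. Look at neighboring provisions.** Section 12.5.2 starts from events that needed 24-hour reporting, yet the annual-report list in 12.5.2.1 includes serious events that are not suspected reactions. That fits a wider intake than 12.5.1 gives. It also fits sponsor downgrading of events the site called related, so it does not settle the intent. Section 12.6 sends every pregnancy to DAIT/NIAID within 1 business day without an attribution filter, so fast reporting of that kind already has a precedent in this protocol.

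**Step 4. Size of the delay.** Assume calendar-month reports. The longest wait is about 31 days. If events fall evenly over the month, the average is 31 / 2 = 15.5 days. Section 12.5.2.2 allows 15 calendar days for expedited reports and 7 for unexpected fatal or immediately life-threatening reactions, so the longest wait exceeds both. It does not state when those clocks start; if they start at sponsor receipt, they are not formally breached.

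**Step 5. Accrual during the delay.** Section 3.1 plans 15 subjects per year, or 1 to 2 per month: 15 / 12 = 1.25 subjects in the longest wait.

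**Step 6. Reach into 11.5.** The thresholds are one related death, 2 participants (ifetroban/placebo or another procedure) and 3 participants (desensitization). A single miscoded death matters by itself. A single miscoded non-fatal event changes the outcome only if 2 − 1 = 1 participant is already counted under the first non-fatal threshold, or 3 − 1 = 2 under the second.

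**The case against.** Three stronger readings are tempting, and the documents support none of them.

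- **That 12.1 and 12.5.1 contradict each other.** Section 12.1 hands the procedure to 12.5 and sets no 24-hour clock. The gap in 12.5 is real, but it is not a flat contradiction.
- **That the sponsor's attribution drives the suspension rule.** Section 12.3.2 limits the sponsor's final determination to safety reporting, and 11.5 names no decision-maker. If the site's attribution governs 11.5, faster reporting does not by itself change the counts.
- **That the monthly listing is the only way anyone outside the site learns of these SAEs.** The ISM reviews all SAEs and communicates safety issues to the NIAID Medical Officer, and 12.5.3 asks for timely reporting to the IRB. Section 12.8.1 also has the Medical Monitor decide on SAE reports. None of these fixes a clock for an SAE coded unrelated: the ISM interval is at least yearly, 12.5.3 gives no number of days, and the Medical Monitor's duty points back to the SAE reporting section.

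It can also be said that the filter is narrow. A possible relationship already counts as related, and the unrelated code requires a documented alternative cause. That stands, but the unlikely code has no such documentation requirement. Finally, the wrong cross-reference in 12.5.1 suggests a drafting slip rather than a considered choice. That may be so; the natural reading of the sentence is still related SAEs only.

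**Conclusion.** The concern holds as a mismatch of scope and a missing timeline. For an SAE the site under-attributes, DAIT/NIAID's final attribution for safety reporting may be delayed by up to about a month, in which about 1.25 subjects (1 to 2 at the planned rate) would enroll. This assumes calendar-month reports, accrual as planned, and no earlier informal notice. The documents give no SAE rate or misattribution rate, so how often this would happen cannot be estimated.

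An effect on the suspension counts is possible but not established, because 11.5 does not say whose attribution governs; that silence needs resolving too. The issue is modest in size and worth correcting, since it concerns safety oversight and the edit is small.

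**What to change.** 1. In 12.5.1, remove the relatedness limit so that all SAEs go to DAIT/NIAID within 24 hours of discovery, with the site's attribution recorded on the form as now.
2. In the same sentence, change the cross-reference for the related categories from 12.2.3 to Table 12.3.2, or drop it if the limit goes.
3. In 11.5, and in the matching synopsis text, state whose attribution counts toward the suspension rule. The thresholds need no change for this purpose.

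Stating a separate deadline for SAEs coded unrelated or unlikely would also close the gap, but it keeps two clocks and still lets the site's code decide which applies.

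The cost is some additional 24-hour SAE forms. With 50 subjects at one site, followed for about 8 weeks each, these are likely to be few, though the documents give no rate to confirm it. The form is already completed for every SAE under 12.4.3 and is sent by email.

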12.5.2 Reporting to Health Authority

After an adverse event requiring 24-hour reporting (per Section 12.5.1, *Reporting of Serious Adverse Events to Sponsor*) is submitted by the site investigator and assessed by DAIT/NIAID, there are two options for DAIT/NIAID to report the adverse event to the appropriate health authorities:

12.5.2.1 Annual Reporting

DAIT/NIAID will include in the annual study report to health authorities all adverse events classified as:

- Serious, expected, suspected adverse reactions (see Section 12.2.1.1, *Suspected Adverse Reaction*, and Section 12.2.2, *Unexpected Adverse Event*).
- Serious and not a suspected adverse reaction (see Section 12.2.2, *Suspected Adverse Reaction*).
- Pregnancies.

Note that all adverse events (not just those requiring 24-hour reporting) will be reported in the Annual DSMB Report.

12.5.2.2 Expedited Safety Reporting

This option, with 2 possible categories, applies if the adverse event is classified as one of the following:

Category 1: Serious and unexpected suspected adverse reaction [SUSAR] (see Section 12.2.1.1, *Suspected Adverse Reaction* and Section 12.2, *Unexpected Adverse Event* and 21 CFR 312.32(c)(1)i).

The sponsor shall report any suspected adverse reaction that is both serious and unexpected.

The sponsor shall report an adverse event as a suspected adverse reaction only if there is evidence to suggest a causal relationship between the study drug and the adverse event, such as:

1. A single occurrence of an event that is uncommon and known to be strongly associated with drug exposure (e.g., angioedema, hepatic injury, or Stevens-Johnson Syndrome);

2. One or more occurrences of an event that is not commonly associated with drug exposure, but is otherwise uncommon in the population exposed to the drug (e.g., tendon rupture);
3. An aggregate analysis of specific events observed in a clinical trial (such as known consequences of the underlying disease or condition under investigation or other events that commonly occur in the study population independent of drug therapy) that indicates those events occur more frequently in the drug treatment group than in a concurrent or historical control group.

Category 2: Any findings from studies that suggests a significant human risk

The sponsor shall report any findings from other epidemiological studies, analyses of adverse events within the current study or pooled analysis across clinical studies or animal or *in vitro* testing (e.g. mutagenicity, teratogenicity, carcinogenicity) that suggest a significant risk in humans exposed to the drug that would result in a safety-related change in the protocol, informed consent, investigator brochure or package insert or other aspects of the overall conduct of the study.

DAIT/NIAID shall notify the FDA and all participating investigators of *expedited Safety* within 15 calendar days; unexpected fatal or immediately life-threatening suspected adverse reaction(s) shall be reported as soon as possible or within 7 calendar days.

12.5.3 Reporting of Adverse Events to IRBs/IECs

All investigators shall report adverse events, including expedited reports, in a timely fashion to their respective IRBs/IECs in accordance with applicable regulations and guidelines. All *Safety Reports to the FDA* shall be distributed by DAIT/NIAID or designee to all participating institutions for site IRB/IEC submission.

12.6 Pregnancy Reporting

The investigator shall be informed immediately of any pregnancy in a study subject or a partner of a study subject. A pregnant subject shall be instructed to stop taking study medication. The investigator shall counsel the subject and discuss the risks of continuing with the pregnancy and the possible effects on the fetus. Monitoring by phone call of the pregnant subject shall continue until one month after the conclusion of the pregnancy.

The investigator shall report to the DAIT/NIAID all pregnancies within 1 business day of becoming aware of the event using the Pregnancy paper CRF. All pregnancies identified during the study shall be followed to conclusion and the outcome of each must be reported. The Pregnancy paper CRF shall be updated and submitted to the DAIT/NIAID when details about the outcome are available. When possible, similar information shall be obtained for a pregnancy occurring in a partner of a study subject.

Information requested about the delivery shall include:

- Gestational age at delivery
- Birth weight, length, and head circumference
- Gender
- Appearance, pulse, grimace, activity, and respiration (APGAR) score at 1 minute, 5 minutes, and 24 hours after birth, if available

- Any abnormalities.

All pregnancy complications that result in a congenital abnormality, birth defect, miscarriage, and medically indicated abortion - an SAE shall be submitted to the DAIT/NIAID using the SAE reporting procedures described above.

12.7 Reporting of Other Safety Information

An investigator shall promptly notify the site IRB as well as the DAIT/NIAID when an “unanticipated problem involving risks to subjects or others” is identified, which is not otherwise reportable as an adverse event.

12.8 Review of Safety Information

12.8.1 Medical Monitor Review

The DAIT/NIAID Medical Monitor shall receive monthly reports from the *Principal Investigator* compiling new and accumulating information on AEs, SAEs, and pregnancies recorded by the study site on appropriate paper CRFs.

In addition, the Medical Monitor shall review and make decisions on the disposition of the SAE and pregnancy reports received by the *Principal Investigator* (See *Reporting of Serious Adverse Events to Sponsor*, and *Pregnancy Reporting*).

12.8.2 ISM Review

12.8.2.1 Planned ISM Reviews

The Independent Safety Monitor (ISM) is a physician who is independent from the study team and will, at minimum, review all SAEs to assess for possible changes to the overall risk of the study. This person will be expected to communicate with the PI and the NIAID Medical Officer regarding any safety issues and may be requested to review study safety documentation.

The ISM shall review safety data at least yearly, which will include, at a minimum, a listing of all reported AEs and SAEs.

12.8.2.2 Ad hoc ISM Reviews

In addition to the pre-scheduled yearly data reviews and planned safety monitoring, the ISM may be called upon for *ad hoc* reviews. The ISM will review any event that potentially impacts safety at the request of the PI or DAIT/NIAID. In addition, the following events will trigger an *ad hoc* comprehensive safety review by the ISM:

- Any death that occurs in the study, which is possibly or definitely related to study treatment regimen.
- The occurrence of a Grade 3 or higher related and unexpected SAE in 3 or more of the study participants who have received a study treatment.

After review of the data, the ISM will make recommendations regarding study conduct and/or continuation.

12.8.3 DSMB Review

12.8.3.1 Planned DSMB Reviews

The Data and Safety Monitoring Board (DSMB) shall review safety data at least yearly during planned DSMB Data Review Meetings. Data for the planned safety reviews will include, at a minimum, a listing of all reported AEs and SAEs.

The DSMB will be informed of an Expedited Safety Report in a timely manner. DSMB notification will occur as soon as site personnel are aware of the event but no later than 72 hours, which aligns with the requirements set forth by institutional guidelines.

12.8.3.2 *Ad hoc* DSMB Reviews

In addition to the pre-scheduled data reviews and planned safety monitoring, the DSMB may be called upon for *ad hoc* reviews. The DSMB will review any event that potentially impacts safety at the request of the protocol chair or DAIT/NIAID. In addition, the following events will trigger an *ad hoc* comprehensive DSMB Safety Review:

- Any death that occurs in the study, which is possibly or definitely related to study treatment regimen.
- The occurrence of a Grade 3 or higher related and unexpected SAE in 3 or more of the study participants who have received a study treatment.

After review of the data, the DSMB will make recommendations regarding study conduct and/or continuation.

